## 7.6. Treatment Compliance

Patient compliance with study medication will be assessed at each visit during the treatment period (Visit 3 through Visit 8) by counting returned tablets.

A patient will be considered significantly noncompliant if he or she misses more than 20% of the prescribed doses of investigational product during the study, unless the patient's investigational product is withheld by the investigator for safety reasons. Similarly, a patient will be considered significantly noncompliant if he or she is judged by the investigator to have intentionally or repeatedly taken 20% more than the prescribed amount of medication during the study.

Patients will be counseled by study staff on the importance of taking the investigational product as prescribed, as appropriate.

Patients' compliance will be further defined in the statistical analysis plan (SAP).

## 7.7. Concomitant Therapy

All concomitant medication, whether prescription or over the counter, used at baseline and/or during the course of the study, must be recorded on the Concomitant Medication electronic case report form (eCRF). Patients will be instructed to consult the investigator or other appropriate study personnel at the site before taking any new medications or supplements during the study. For AD therapies permitted as part of rescue therapy, see Section [7.7.3](#).

### 7.7.1. Prohibited Medications and Procedures

#### Prohibited Medications and Procedures Not Requiring Interruption of Investigational Product

The following therapies will not be allowed during the course of the study and, if taken by or administered to the patient, the prohibited therapy must be discontinued.

- TCS, TCNIs (e.g., tacrolimus and pimecrolimus), or topical PDE 4 inhibitor (i.e., crisaborole) except when given as rescue therapy as described in Section [7.7.3](#).
- topical antihistamines or sedating, systemic antihistamines including, but not limited to, alimemazine, chlorphenamine, clemastine, cyproheptadine, diphenhydramine, hydroxyzine, ketotifen, and promethazine
- leukotriene inhibitors (e.g., montelukast [Singulair], zafirlukast [Accolate], and zileuton [Zyflo])
- allergen immunotherapy

- phototherapy including PUVA (psoralen and ultraviolet A), ultraviolet B, tanning booth and excimer laser
- bleach baths

### **Prohibited Medications Requiring Temporary Interruption of Investigational Product**

The following therapies will not be allowed during the course of the study and, if taken by or administered to the patient, temporary interruption of investigational product is required.

- live vaccines (including Bacillus Calmette-Guérin [BCG] or herpes zoster), (see Exclusion Criterion [27])
  - For BCG vaccination, investigational product should be temporarily interrupted for 12 weeks.
  - For herpes zoster vaccination, investigational product should be temporarily interrupted for 4 weeks.
- probenecid: if a patient is inadvertently started on probenecid, IP should be temporarily interrupted, and can be resumed after patient has discontinued probenecid. If a patient is not able to discontinue probenecid, then IP should be permanently discontinued

### **Prohibited Medications Requiring Permanent Discontinuation of Investigational Product**

- systemic corticosteroids
- any systemic therapy, investigational or commercial (approved or off label use), used for the treatment of AD or symptoms of AD (except for antihistamines, as specified above)
- other JAK inhibitors (e.g., tofacitinib and ruxolitinib)
- systemic immunosuppressive/immunomodulatory substances, including, but not limited to, cyclosporine, methotrexate, mycophenolate mofetil, interferon  $\gamma$ , azathioprine, or biologic agents

Note: In the event that these prohibited medications were inadvertently used, agreement and documentation to continue investigational product must be sought from sponsor.

### **7.7.2. Permitted Medications and Procedures**

Treatment with concomitant AD therapies during the study is permitted only as described below.

- Daily use of emollients is required as background treatment. Moisturizers with additives such as antipruritics or antiseptics are not permitted. If daily applications are missed, it will not be considered a protocol violation.
  - Patients should not apply emollients on the day of their study visit prior to the procedures to allow adequate assessment of skin dryness.
- For those patients on stable dosing of prescription sleep medications at entry, downward dose adjustments or discontinuation of treatment may occur during the study.

- Nonsedating antihistamines including, but not limited to, acrivastine, bilastine, cetirizine, desloratadin, fexofenadine, levocetirizine, loratadine, mizolastine, and rupatadine are allowed.
- Single intra-articular or soft tissue (bursa, tendons, and ligaments) corticosteroid injection is allowed during the 16-week double-blind, placebo-controlled period.
- Intranasal or inhaled steroid use is allowed.
- Topical anesthetics and topical and systemic anti-infective medications are allowed.
- Nonlive seasonal vaccinations and/or emergency vaccination, such as rabies or tetanus vaccinations, are allowed.

Any changes of these concomitant medications must be recorded in the Concomitant Therapy of Special Interest eCRF.

Treatment with concomitant therapies for other medical conditions such as diabetes and hypertension is permitted during the study.

### **7.7.3. *Rescue Therapy***

#### **Criteria for rescue therapy initiation**

Investigators should attempt to manage patients with emollients, however, investigators are allowed to rescue patients who are experiencing unacceptable or worsening symptoms of AD at any time. Prior to rescue, it is recommended that increased frequency of emollient use is attempted to at least twice a day or more in an effort to control symptoms. The rationale for rescue will be documented.

#### **Choice of rescue therapy treatment**

- Triamcinolone 0.1% cream and/or hydrocortisone 2.5% ointment. Where possible, both of these treatments will be supplied by the sponsor. In the event where providing 1 or both of these topical formulations is not possible, an alternate, equivalent potency TCS cream and/or ointment may be provided by the sponsor. TCS use, supplied by the sponsor, should be recorded via weight of returned tubes as indicated in the Schedule of Activities (Section 2).
  - In the event that the sponsor is unable to supply TCS, commercially available triamcinolone 0.1% cream and/or hydrocortisone 2.5% ointment may be supplied by the sites. Where providing triamcinolone 0.1% cream and/or hydrocortisone 2.5% ointment is not possible, an equivalent-potency TCS cream and/or ointment that is in line with local practices can be supplied. Refer to [Appendix 7](#) for guidance on potency equivalence.
  - If the TSC supplied by the sponsor is not considered suitable for an individual patient, an equivalent-potency TCS cream and/or ointment that is in line with

local practices can be supplied by the sites. Refer to [Appendix 7](#) for guidance on potency equivalence.

- Investigators may also select to use TCNIs and/or crisaborole where approved, although use of either during the study is neither encouraged nor provided. If TCNIs are prescribed, use should be limited to problem areas only (e.g., face, neck, skin folds, genital areas, etc.).
- On the days of study visits, topical therapy should not be applied before the patient has undergone all study procedures and clinical evaluations in order to allow adequate assessment of skin dryness
- Patients rescued to topical therapy will continue to take investigational product and use of rescue therapy will be documented in the eCRF.

In patients who do not improve sufficiently with the provided rescue topical therapy after 7 days, a higher potency TCS may be used (see [Appendix 7](#)) and investigational product may continue. Higher potency TCS will not be supplied centrally by the sponsor. It is recommended that if a patient reaches “clear” to “almost clear” skin after topical rescue, then medium- and/or high-potency TCS and TCNI should be stopped, and low-potency TCS (e.g., hydrocortisone 2.5% ointment) should be used once daily for an additional 7 days, then stopped. If lesions return, patients can be retreated with TCS with or without TCNIs and/or crisaborole as before at the discretion of the investigator.

If topical rescue therapy as described above fails to sufficiently control AD symptoms, then oral systemic medications may be used as rescue (e.g., corticosteroids, cyclosporine, methotrexate); however, investigational product will be required to be permanently discontinued for the remainder of the 16-week study duration. If these medications are needed for other medical conditions (e.g., asthma flare), they will still be treated as rescue medications. These patients are still eligible to enter the long-term extension study (JAHN), if they complete the schedule of study visits through Visit 8 (Week 16) and are also able to complete a minimum 4-week washout from oral systemic rescue medications (which can occur during the screening period for Study JAHN).

Investigators should make every attempt to conduct efficacy and safety assessments immediately before administering any rescue treatment. An unscheduled visit can be used for this purpose if necessary.

## 7.8. Treatment after the End of the Study

### 7.8.1. Study Extensions

Patients who complete this study through Visit 8 may be eligible to participate in Study JAHN, if enrollment criteria for Study JAHN are met.

### **7.8.2. *Continued Access***

After the conclusion of the study, continued access to baricitinib will not be provided to patients who are not eligible for or who do not choose to participate in Study JAHN. Patients will be referred to their local treatment centers for AD therapy as clinically indicated.

## 8. Discontinuation Criteria

### 8.1. Discontinuation from Study Treatment

#### 8.1.1. *Temporary Interruption from Investigational Product*

In some circumstances, it may be necessary to temporarily interrupt treatment as a result of AEs or abnormal laboratory values that may have an unclear relationship to investigational product. For example, investigational product should be temporarily interrupted if the patient experiences a cardiovascular adverse event considered to be related to study treatment, is graded as moderate (Grade 2 according to Common Terminology Criteria for Adverse Events [CTCAE] Version 3.0), and that does not resolve promptly with supportive care. Except in cases of emergency, it is recommended that the investigator consult with Lilly (or its designee) before temporarily interrupting therapy for reasons other than those defined in [Table JAHL.4](#).

For the abnormal laboratory findings and clinical events (regardless of relatedness) listed in [Table JAHL.4](#), specific guidance is provided for temporarily interrupting treatment and when treatment may be restarted. Retest frequency and timing of follow-up laboratory tests to monitor the abnormal finding is at the discretion of the investigator. Investigational product that was temporarily interrupted because of an AE or abnormal laboratory value not specifically covered in [Table JAHL.4](#) may be restarted at the discretion of the investigator.

**Table JAHL.4. Criteria for Temporary Interruption of Investigational Product**

Hold Investigational Product if the Following Laboratory Test Results or Clinical Events Occur:	Investigational Product May Be Resumed When:
WBC count <2000 cells/ $\mu$ L ( $<2.00 \times 10^3/\mu\text{L}$ or $<2.00 \text{ GI/L}$ )	WBC count $\geq 2500$ cells/ $\mu$ L ( $\geq 2.50 \times 10^3/\mu\text{L}$ or $\geq 2.50 \text{ GI/L}$ )
ANC <1000 cells/ $\mu$ L ( $<1.00 \times 10^3/\mu\text{L}$ or $<1.00 \text{ GI/L}$ )	ANC $\geq 1200$ cells/ $\mu$ L ( $\geq 1.20 \times 10^3/\mu\text{L}$ or $\geq 1.20 \text{ GI/L}$ )
Lymphocyte count <500 cells/ $\mu$ L ( $<0.50 \times 10^3/\mu\text{L}$ or $<0.50 \text{ GI/L}$ )	Lymphocyte count $\geq 750$ cells/ $\mu$ L ( $\geq 0.75 \times 10^3/\mu\text{L}$ or $\geq 0.75 \text{ GI/L}$ )
Platelet count <75,000/ $\mu$ L ( $<75 \times 10^3/\mu\text{L}$ or $<75 \text{ GI/L}$ )	Platelet count $\geq 100,000/\mu\text{L}$ ( $\geq 100 \times 10^3/\mu\text{L}$ or $\geq 100 \text{ GI/L}$ )
eGFR <40 mL/min/1.73 m  (from serum creatinine) for patients with screening eGFR $\geq 60$ mL/min/1.73 m 	eGFR $\geq 50$ mL/min/1.73 m 
eGFR <30 mL/min/1.73 m  (from serum creatinine) for patients with screening eGFR $\geq 40$ to $<60$ mL/min/1.73 m 	eGFR $\geq 40$ mL/min/1.73 m 
ALT or AST >5x ULN	ALT and AST return to $<2 \times$ ULN, and IP is not considered to be the cause of enzyme elevation
Hemoglobin <8 g/dL ( $<80.0 \text{ g/L}$ )	Hemoglobin $\geq 10$ g/dL ( $\geq 100.0 \text{ g/L}$ )
Symptomatic herpes zoster	All skin lesions have crusted and are resolving
Infection that, in the opinion of the investigator, merits the IP being interrupted	Resolution of infection
Clinical features of VTE (such as deep vein thrombosis or pulmonary embolism) are present a	After evaluation and institution of appropriate treatment of VTE b

Abbreviations: ALT = alanine aminotransferase; ANC = absolute neutrophil count; AST = aspartate aminotransferase; eGFR = estimated glomerular filtration rate; IP = investigational product; ULN = upper limit of normal; VTE = venous thromboembolic event; WBC = white blood cell.

- a Evaluate promptly and institute appropriate treatment. If upon evaluation VTE is ruled out and no other temporary or permanent discontinuation criteria are met, then IP may be resumed.
- b If after evaluation and institution of treatment the investigator deems that the patient is still at significant risk, or if this would constitute a second VTE for the patient, then IP should be discontinued permanently

Although temporary interruption of investigational product is not a requirement at times of increased potential risk of VTE (e.g., surgery, significant air travel, or other situations involving prolonged immobilization) we recommend following appropriate VTE prophylaxis guidelines to help manage the VTE risk under these circumstances.

For specific guidance on temporary interruption of IP after use of a prohibited medication, please refer to Section [7.7.1](#) (Prohibited Medications and Procedures).

Lastly, investigational product should be temporarily interrupted for suicidal ideation or any suicide-related behaviors as assessed by the following patient responses on the C-SSRS:

- A “yes” answer to Question 4 (Active Suicidal Ideation with Some Intent to Act, Without Specific Plan) **or**
- A “yes” answer to Question 5 (Active Suicidal Ideation with Specific Plan and Intent) on the “Suicidal Ideation” portion of the C-SSRS **or**
- A “yes” answer to any of the suicide-related behaviors (actual attempt, interrupted attempt, aborted attempt, preparatory act or behavior) on the “Suicidal Behavior” portion of the C-SSRS.

NOTE: Prior to resumption of investigational product, it is recommended that a patient be assessed by a psychiatrist or appropriately trained professional to assist in deciding whether the subject should remain on investigational product and ultimately continued participation in the study. A patient does not necessarily have to have investigational product interrupted if they have self-injurious behavior that would be classified as non-suicidal self-injurious behavior.

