#### **9.4.9. *Hepatic Safety Monitoring and Data Collection***

If a study patient experiences elevated ALT  $\geq 3$ x ULN, ALP  $\geq 2$ x ULN, or elevated TBL  $\geq 2$ x ULN, liver testing (Appendix 4) should be repeated within 3 to 5 days including ALT, AST, ALP, TBL, direct bilirubin, gamma-glutamyl transferase, and creatine kinase to confirm the abnormality and to determine if it is increasing or decreasing. If the abnormality persists or worsens, clinical and laboratory monitoring should be initiated by the investigator and in consultation with the study medical monitor. Monitoring of ALT, AST, TBL, and ALP should continue until levels normalize or return to approximate baseline levels.

Discontinuation criteria of investigational products, either temporary interruption or permanent discontinuation, due to abnormal ALT, AST, TBL, or ALP, are detailed in Section 8.1.

Additional safety data should be collected via the hepatic eCRF if 1 or more of the following conditions occur:

- elevation of serum ALT to  $\geq 5$ x ULN on 2 or more consecutive blood tests
- elevated serum TBL to  $\geq 2$ x ULN (except for cases of known Gilbert’s syndrome)
- elevation of serum ALP to  $\geq 2$ x ULN on 2 or more consecutive blood tests
- patient discontinued from treatment due to a hepatic event or abnormality of liver tests
- hepatic event considered to be an SAE.

See [Appendix 4](#) and [Appendix 5](#) for a description of hepatic laboratory values that warrant exclusion from the study, temporary or permanent discontinuation of investigational product, or additional safety collection via the hepatic eCRF.

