## Appendix 5. Liver Function Testing and Hepatic Safety Monitoring

### Liver Function Testing and Hepatic Safety Monitoring

Analyte	Exclusion Criteria	Additional Hepatic Testing	Hepatic eCRF Reporting	Temporary Interruption of IP	Permanent Discontinuation of IP after Consultation with the Lilly-Designated Medical Monitor
Protocol Section	Section 6.2	Section 9.4.9	Section 9.4.9	Section 8.1.1	Section 8.1.2
ALT/AST	$\geq 2x$ ULN	$\geq 3x$ ULN	$\geq 5x$ ULN on $\geq 2$ consecutive tests	$\geq 5x$ ULN	
 
• <math>>8x</math> ULN
 
• <math>>5x</math> ULN for <math>>2</math> weeks
 
• <math>>3x</math> ULN AND TBL <math>>2x</math> ULN or INR <math>>1.5</math>
 
• <math>>3x</math> ULN with symptomsa
 

ALP	$\geq 2x$ ULN	$\geq 2x$ ULN	$\geq 2x$ ULN on $\geq 2$ consecutive tests	No applicable criteria	
 
• <math>>3x</math> ULN
 
• <math>>2.5x</math> ULN AND TBL <math>>2x</math> ULN
 
• <math>>2.5x</math> ULN with symptomsa
 

TBL	$\geq 1.5x$ ULN	$\geq 2x$ ULN	$\geq 2x$ ULN (excluding Gilbert's syndrome)	No applicable criteria	
 
• ALT <math>>3x</math> ULN AND TBL <math>>2x</math> ULN
 
• ALP <math>>2.5x</math> ULN AND TBL <math>>2x</math> ULN
 

Abbreviations: ALP = alkaline phosphatase; ALT = alanine aminotransferase; AST = aspartate aminotransferase;

INR = international normalized ratio; IP = investigational product; TBL = total bilirubin level; ULN = upper level of normal.

a Fatigue, nausea, vomiting, right upper-quadrant pain or tenderness, fever, rash, and/or eosinophilia ( $>5\%$ ).

---

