When criteria are met for hepatic evaluation and completion of the hepatic safety CRF, investigators are required to answer a list of questions (see Compound level safety standards). A listing of the collected information will be generated together with a graphical patient profile. This includes demographics, disposition, and a display of study drug exposure, AEs, medications, and the liver-related measurements over time will be provided for these patients and any additional patients meeting ALT or AST measurement greater than or equal to $5 \times$ ULN (on a single measurement) or ALP measurement greater than or equal to $2 \times$ ULN (on a single measurement).

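### Section 9.4.9 triggers repeat liver testing and the hepatic eCRF on ALT but not AST, while Appendix 5, citing that section, applies both triggers to ALT/AST

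*Protocol*

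**What the plan says.** **Repeat testing.** Protocol Section 9.4.9 opens with "If a study patient experiences elevated ALT $\geq 3$ x ULN" and adds ALP and total bilirubin, each at 2x ULN or more. AST is in the panel that is then repeated and in the later monitoring, but an AST value does not start the process.

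**Hepatic eCRF.** The aminotransferase condition in Section 9.4.9 is "elevation of serum ALT to $\geq 5$ x ULN on 2 or more consecutive blood tests". The other conditions are raised total bilirubin, raised ALP on consecutive tests, discontinuation of treatment for a hepatic reason, and a serious hepatic event. No condition names AST.

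**Appendix 5.** The same section sends the reader to Appendices 4 and 5 "for a description of hepatic laboratory values that warrant exclusion from the study, temporary or permanent discontinuation of investigational product", and for the values that call for the hepatic eCRF. Appendix 5 has a single ALT/AST row. Its additional-testing and eCRF columns both cite Section 9.4.9. They give at least 3x ULN, and at least 5x ULN on two or more consecutive tests.

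**Interruption.** Table JAHL.4 in Section 8.1.1 holds investigational product at "ALT or AST >5x ULN". The Appendix 5 column citing Section 8.1.1 gives at least 5x ULN for ALT/AST.

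**The concern.** Appendix 5 names Sections 8.1.1 and 9.4.9 as its sources, and Section 9.4.9 refers back to it, so the texts should state the same rules. They do not, and neither the sections nor the appendix says which governs.

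What is at stake is uniform safety follow-up. Hepatic events are adverse events of special interest (Section 9.2.2). If one site works from Section 9.4.9 and another from Appendix 5, the early retest and the hepatic form will be obtained for AST-only rises at one site and not at the other. The SAP (Section 6.14.5.1) lists the form's answers for patients who met the form's criteria. Answers that were never collected cannot be recovered at analysis.

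**Working it through.** No formula applies. The check sets each rule beside its counterpart.

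| Action | Sections 8.1.1 and 9.4.9 | Appendix 5 | Where they part |
|---|---|---|---|
| Repeat liver tests | ALT ≥3x ULN | ALT/AST ≥3x ULN | AST ≥3x with ALT below 3x |
| Hepatic eCRF | ALT ≥5x ULN, 2 or more consecutive tests | ALT/AST ≥5x ULN, 2 or more consecutive tests | AST meets the rule, ALT does not |
| Temporary interruption | ALT or AST >5x ULN | ALT/AST ≥5x ULN | Exactly 5x ULN |

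The ALP and bilirubin triggers for retesting and for the eCRF agree between the two texts, so the gap is confined to AST.

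1. **Retest.** Take AST ≥3x ULN with ALT below 3x, and with ALP and bilirubin both below 2x. Appendix 5 calls for the repeat panel and Section 9.4.9 does not. In the Schedule of Activities, post-baseline chemistry during treatment falls at Weeks 4, 8, 12 and 16. Without the retest, the next planned measurement is nominally 4 weeks away (8 − 4 = 12 − 8 = 16 − 12 = 4), against 3 to 5 days with it.

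2. **eCRF.** Take AST ≥5x ULN on two consecutive tests, with ALT not meeting that rule and no other condition met. Appendix 5 calls for the form and Section 9.4.9 does not. The first gap feeds the second: where no early retest is prompted, the second consecutive AST value may come later or not at all.

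3. **Interruption.** Below 5x both texts leave drug running, and above 5x both hold it. Only a result of exactly 5x ULN separates them.

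4. **Superseded text?** No. The amendment (a) summary lists a change to the VTE row of Table JAHL.4 and none to these hepatic thresholds.

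5. **Reach into the SAP.** Section 6.14.5.1 summarises AST at 3x, 5x and 10x ULN, plots maximum AST against bilirubin, and lists potential Hy's rule cases on either enzyme. It also gives profiles for any additional "patients meeting ALT or AST measurement greater than or equal to $5 \times$ ULN (on a single measurement"). None of these needs the hepatic form. Only the form's own answers and the timing of extra tests depend on the trigger.

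**The case against.** The best defence is that Section 9.4.9 omits AST as a trigger without excluding it. It includes AST in the repeat panel and refers the reader to Appendix 5, which covers it. Read together, the two could be complementary. That is a fair reading, but it depends on each site supplying it. Section 9.4.9 lists its triggers explicitly, and Appendix 5 presents itself as a digest of that section, not an addition to it.

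On interruption, the defence is that Section 8.1.1 makes Table JAHL.4 the specific guidance, so sites have a working rule. Since the two signs part only at exactly 5x ULN, little turns on this.

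Three stronger readings are tempting, and the documents do not support them.

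- A reader might infer that every AST-only rise at or above 5x ULN is lost to the hepatic eCRF under Section 9.4.9. Both texts require two or more consecutive tests. The form is also reached through a serious hepatic event or discontinuation for a liver abnormality, and under Section 8.1.2 AST above 5x ULN for more than 2 weeks is itself grounds to consider discontinuation.
- A reader might infer that AST above 5x ULN could go unmeasured afterwards. Table JAHL.4 holds drug and makes resumption depend on both ALT and AST falling below 2x ULN. AST must therefore be measured again before restart, although Section 8.1.1 leaves the timing to the investigator.
- A reader might infer that hepatic safety data as a whole depend on which page a site follows. Scheduled chemistry and the planned AST displays do not.

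**Conclusion.** The inconsistency is real, stands in the current text, and is narrow. It covers two groups: patients with an AST-only rise of at least 3x ULN, for the early retest; and patients with AST-only values of at least 5x ULN on consecutive tests and no other reason for the form, for the eCRF. The difference in interruption sign is a minor second point.

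The number of patients affected cannot be estimated, because the documents give no expected frequency of AST-only rises. Type I error, power and the efficacy analyses are untouched.

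The conclusion assumes that ALT/AST in Appendix 5 means either enzyme. The interruption point also depends on the > and ≥ signs, which should be confirmed against the source page. The ALT versus ALT/AST point does not depend on them.

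**What to change.** Issue a protocol clarification that reconciles Section 9.4.9, Table JAHL.4 and Appendix 5: one set of aminotransferase triggers for the retest and for the eCRF, and one sign for interruption at 5x ULN. State which text governs if a difference remains, and tell sites. The choice of rule is the sponsor's, and none is proposed here.

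In the same pass, check the bilirubin row of Appendix 5. For permanent discontinuation it pairs raised bilirubin with ALT alone, where Section 8.1.2 and the ALT/AST row use either enzyme.

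The cost is a wording change and a site notice, with no change to design, sample size or planned SAP tables. If the data are already collected, the study report can state which trigger sites applied and how many patients had AST-only rises without a hepatic form.
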